5.2.2.3. Other Secondary Efficacy Endpoints in the RW Period and Statistical Method

All time-to-event endpoints start from the day of randomization. The same censoring rules for the primary endpoint will be applied. Missing values will not be imputed unless otherwise specified. Analysis of secondary endpoints will be based on ITT analysis unless otherwise specified.

1. Proportion of subjects who maintained Clinical Response at Week 24 of the RW period based on ITT Week 24 analysis set

The same rules and method for the first major secondary endpoint will be applied, except that 16 weeks is replaced with 24 weeks.

2. Proportion of subjects who maintained Clinical Response at Week 8 of the RW period based on based on ITT Week 8 analysis set

The same rules and method for the first major secondary endpoint will be applied, except that 16 weeks is replaced with 8 weeks.

3. Percentage of days with minimal or no pain in the first 24 weeks post randomization based on ITT Week 24 analysis set

The same rules and method for the second major secondary endpoint will be applied, except that 16 weeks is replaced with 24 weeks.

4. Percentage of days with minimal or no pain in the first 8 weeks post randomization based on ITT Week 8 analysis set

The same rules and method for the second major secondary endpoint will be applied, except that 16 weeks is replaced with 8 weeks.

5. Proportion of subjects with absent or minimal pericarditis symptoms (based on the 7-point PGIPS) at Week 24 of the RW period based on subjects who were randomized at least 24 weeks before data cutoff

The same rules and method for the third major secondary endpoint will be applied, except that 16 weeks is replaced with 24 weeks.

6. Proportion of subjects with absent or minimal pericarditis symptoms (based on the 7-point PGIPS) at Week 8 of the RW period based on subjects who were randomized at least 8 weeks before data cutoff

The same rules and method for the third major secondary endpoint will be applied, except that 16 weeks is replaced with 8 weeks.

7. Proportion of subjects without pericarditis recurrence in the first 24 weeks of the RW period

The proportion of subjects without pericarditis recurrence in the first 24 weeks of the RW period in each arm will be estimated using the KM method, as described in the

analysis of the primary endpoint. The same censoring rules will apply. The variance of the difference in proportion between treatment arms will be the sum of the variance in each arm. The p-value and 95% CI will be calculated using a normal approximation.

8. Time to pericarditis pain NRS ≥ 4

Use the same method for the primary endpoint.

9. Time to CRP level ≥ 1 mg/dL. This is for elevation of CRP for causes.

Use the same method for the primary endpoint. A manual review for any CRP ≥ 1 mg/dL will be performed to make sure that the CRP increase was caused by pericarditis.

10. Time to pericardial rub

Use the same method for the primary endpoint. Subjects with pericardial rub at RW baseline will be excluded from the analysis.

11. Time to widespread ST-segment elevation or PR-segment depression on ECG

Use the same method for the primary endpoint. Subjects with either condition at RW baseline will be excluded.

12. Time to new or worsening pericardial effusion on ECHO

Use the same method for the primary endpoint. Proportion of subjects with new or worsening in pericardial effusion on ECHO and its 95% CI in each arm will be estimated using the K-M method.

13. Change in category of ECHO pericardial effusion size at week 24 and end of RW based on central labs

- The ITT Week 24 analysis set will be used for this endpoint. Effusion size in ECHO has the following categories:
- None or Trivial/Physiologic
- Small
- Moderate
- Large
- Very Large
- NM/ND (Not Measurable/Not Recorded by Site)

Shift tables for change from RW baseline to RW weeks 24 and to end of RW visit will be generated. Due to potentially different number of subjects receiving bailout rilonacept between treatment arms, there will be no hypothesis testing for this endpoint.

Endpoints 14-16 will be summarized for data before receiving bailout rilonacept and

for data including bailout riloncept in each arm. P-values will not be provided due to potentially different number of subjects receiving bailout riloncept.

14. Change over time in central-lab CRP level

A mixed model with repeated measures (MMRM) using TYPE=UN option in SAS Proc Mixed will be applied in the analysis of this endpoint. If the model does not converge, an analysis of covariance (ANCOVA) model will be used at each timepoint to calculate least-squares (LS) means. In the model, subjects will have repeated measures for the response variable change from baseline of the endpoint. The explanatory variables will include the baseline value, treatment arm, baseline value by treatment interaction, and the variables for randomization strata. Only observed values will be used in the analysis without imputation.

15. Change over time in the subject's assessments of pericarditis pain (weekly averages)

The same method for change over time in CRP level will be applied. If bailout riloncept is used in a week, the week will be considered as after bailout.

16. Number (percentage) of subjects with absent or minimal pericarditis activity over time after RW week 24 based on the PGIPS. The denominator in each arm will be the total number of subjects with the assessment at each visit.

17. Number (percentage) of subjects with absent or minimal pericarditis activity over time based on the PGA-PA. The denominator in each arm will be the total number of subjects with the assessment at each visit.

The same analysis method and analysis sets for PGPIS will be applied.

The endpoints below (18 – 23) from patient reported outcomes will be summarized with descriptive statistics. There will be no hypothesis testing since they are measured at RW baseline and Week 24 only and receiving bailout riloncept due to recurrence at Week 24 could be a confounding factor.

18. Change from baseline to week 24 in the SF-36 Physical and Mental Component Scores (see below for definition)

19. Change from baseline to week 24 in Physical Functioning, Role-Physical, Bodily Pain, General Health, Vitality, Social Functioning, Role-Emotional, and Mental Health domains in SF-36.

The SF-36v2[®] Health Survey (standard, four-week recall) is a 36-item generic (not indication specific) instrument used to evaluate subject reported health related quality of life (HRQoL) in adult subjects. The questions are organized in eight health domain scales: physical functioning [PF] (10 items), role participation with physical health problems [RP] (four items), bodily pain [BP] (two items), general health status [GH] (one item), vitality [VT] (four items), social functioning [SF] (two items), role participation with emotional health problems [RE] (three items), and mental health (five items). Scores from the eight domains are summarized into a physical component score (PCS) and mental component score (MCS).

The SF-36v2 utilizes norm-based scoring involving a linear T-score transformation

method so that scores for each of the health domain scales and component summary measures have a mean of 50 and a standard deviation of 10, based on the 2009 United States general population. Scores above and below 50 are above and below the average, respectively, in the 2009 United States general population. Also, because the standard deviation is 10, each 1-point difference or change in scores has a direct interpretation; that is, 1 point is one-tenth of a standard deviation, or an effect size of 0.10.

Subject responses will be scored, including the handling of missing data, consistent with the instructions in the SF-36v2 user manual using the Optum Smart Measurement System Scoring Solution software.

The possible score for each item is from 1 to 6. Each item response is then assigned a numeric value according to one of 8 scales.

Items 1, 2, 20, 22, 34, 36: 1=100, 2=75, 3=50, 4=25, 5=0

Items 3, 4, 5, 6, 7, 8, 9, 10, 11, 12: 1=0, 2=50, 3=100

Items 13, 14, 15, 16, 17, 18, 19: 1=0, 2=100

Items 21, 23, 26, 27, 30: 1=100, 2=80, 3=60, 4=40, 5=20, 6=0

Items 24, 25, 28, 29, 31: 1=0, 2=20, 3=40, 4=60, 5=80, 6=100

Items 32, 33, 35: 1=0, 2=25, 3=50, 4=25, 5=0.

Final scores for each scale range from 0 to 100 with higher scores indicating better health. If a subject does not respond to a question, the average score for an item will use the number of non-missing scores for the denominator.

[Table 2](#) displays the items that are categorized. Detailed information can be found in Mark, EM (2011).

Table 2: The 8 Domains in SF-36v2

Scale	Number of items	After recoding, average the following items
Physical functioning	10	3 4 5 6 7 8 9 10 11 12
Role-physical (RP)	4	13 14 15 16
Bodily pain	2	21 22
General health	5	1 33 34 35 36
Vitality	4	23 27 29 31
Social functioning	2	20 32
Role-emotional (RE)	3	17 18 19
Mental health	5	24 25 26 28 30

20. Changes in SF-6D utility index score

The SF-6D is calculated based on responses to 11 items on the SF-36, that correspond

to 6 domains: physical functioning, role participation (combined role-physical and role-emotional), social functioning, bodily pain, mental health, and vitality.

RP and RE are combined, and general health is not included. The specific SF-36v2 areas or activities contributing to the scoring of this index include:

- ability to engage in both moderate and vigorous activities
- ability to bathe and dress oneself
- limitations in the kind of work or other activities as the result of physical health; accomplishing less due to emotional problems
- bodily pain and its interference with normal work; nervousness, depression, and energy level
- interference with social activities due to physical or emotional problems.

Individual respondents can be classified on any of four to six levels of functioning or limitations for each of six domains, thus allowing a respondent to be classified into any of 18,000 possible unique health states. Using a standard gamble technique, each of these health states were mapped onto the SF-6D index score, which ranges from 0.00 (worst possible health state/death) to 1.00 (best possible health state/perfect health).

The PRO Analytics software calculates and outputs the SF-6D for each subject at each assessment, just as it does for the 8 domain scores and 2 summary scores.

In the 2009 QualityMetric US Normative survey (Maruish 2011), from which the scoring algorithms were derived, the SF-6D calculated for 3,856 participants who completed the standard (4-week recall) form of the SF-36v2 had a mean of 0.74 and a SD of 0.14. Based on a paper from Walters and Brazier (2003), a change of 0.05 in the SF-6D would indicate a minimally important difference.

Table 3: SF-36v2 Health Survey Items Scored for the SF-6D

SF-6D Domains	SF-36v2™ Health Survey Items
Physical Functioning	3a, 3b, 3j
Role Participation (RP & PE)	4c, 5b
Social Functioning	10
Bodily Pain	7, 8
Mental Health	9b, 9f
Vitality	9e

21. Change in EQ-5D-5L individual scores and index value

The EQ-5D-5L is a subject reported health status utility index for adult subjects that is comprised of five questions plus a visual analog scale (VAS). The five questions ask the respondent to assess their health in terms of mobility, self-care, usual activities,

pain/discomfort, and anxiety/depression. The VAS captures the respondent's self-reported level of the health on the day of completion, captured as a numeric input from 0 ('the worst health you can imagine') to 100 ('the best health you can imagine'). Subject responses will be scored, including the handling of missing values, as specified in the EuroQol Research Foundation, EQ-5D-5L User Guide, 2019, available from <http://euroqol.org/publications/user-guides>.

Scores from the five questions will be reported individually and converted to a single index value using the value set for US. Health state index scores generally range from less than 0 (where 0 is the value of a health state equivalent to dead; negative values representing values as worse than dead) to 1 (the value of full health), with higher scores indicating higher health utility.

22. Change in subject's sleep quality assessed with the Insomnia Severity Index (ISI).

The ISI is a 7-item self-report questionnaire assessing the nature, severity, and impact of insomnia. The usual recall period is the "last 2 weeks" and the dimensions evaluated are severity of sleep onset, sleep maintenance, early morning awakening problems, sleep dissatisfaction, interference of sleep difficulties with daytime functioning, noticeability of sleep problems by others, and distress caused by the sleep difficulties. A 5-point Likert scale is used to rate each item (e.g., 0=no problem; 4=very severe problem), yielding a total score ranging from 0 to 28 (Morin et al 2011).

The ISI will be collected in subjects ≥ 18 years or older as described in the protocol.

23. Change in ISI categories. The ISI total scores are divided to 4 categories:

- 1) 0–7 = No clinically significant insomnia
- 2) 8–14 = Subthreshold insomnia
- 3) 15–21 = Clinical insomnia (moderate severity)
- 4) 22–28 = Clinical insomnia (severe)

A shift table will also be used to summarize the changes over time.

24. Cumulative number (percentage) of subjects who received sequential ORT, corticosteroid, or bailout riloncept for pericarditis period every 4 weeks cumulatively in the RW period.

The CMH test stratified by the randomization strata will be applied to this endpoint.

25. Proportion of subjects using ORT (analgesics, NSAIDs, and/or colchicine) for pericarditis in the first 24 weeks. ORT use while waiting for at least 5 days since previous administration of study medication before receiving bailout riloncept or within 5 days prior to the assessment of pericarditis recurrence visit is excluded. The denominator of the percentages is the number of subjects in the ITT analysis set in each arm. There will be no hypothesis testing for this endpoint.

26. The endpoints below for MRI assessments will be summarized at RW baseline and week 24. P-values will not be calculated.

- Proportion of subjects with pericardial delayed hyperenhancement

- Proportion of subjects with myocardial delayed hyperenhancement
- Proportion of subjects with pericardial effusion, and effusion size

A subject will have pericardial effusion if the effusion size is rated “Small” or larger.

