2.3. Sample Size Calculation and Randomization

2.3.1. Sample Size Calculation

Sample size calculation is based on the primary endpoint, time to pericarditis recurrence defined as the time from randomization to the date of the first pericarditis recurrence for each subject. Time to pericarditis recurrence is assumed to follow an exponential distribution. An event of interest is defined as a subject's first adjudicated recurrence of pericarditis. The following assumptions are used in the sample size calculation using EAST 6.4.1:

- 1-sided significance level: 2.5%
- Power: 90%
- Median time to event (in weeks) in placebo: 8
- Hazard ratio (rilonacept/placebo): 0.244
- Percentage of subjects in the RI period that will not reach RW: 10%.

Given these assumptions, a total of 22 adjudicated pericarditis recurrence events is required to achieve the power. About 25 subjects per arm (a total of 50 subjects) or more will be randomized. Considering 10% of subjects in the RI period that will not reach the RW period, approximately 56 subjects will be enrolled in this study.

Subject enrollment and the pericarditis recurrence event accrual will be closely monitored during the study. The monitoring activities will be done in a blinded fashion during the RW period. If the number of subjects randomized is less than 50 and/or the time anticipated for the number of events required for the analysis of primary efficacy endpoint significantly exceeds the projected timeline, additional subjects may be enrolled and/or randomized at Kiniksa Pharmaceutical's discretion. However, at this time it is anticipated that no more than 100 subjects will be enrolled into this study.

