2.4. Timing of Analysis

The data cutoff for the primary analysis will be the end of RW period. When at least 22 adjudicated pericarditis recurrence events have occurred, end of RW period will be announced. The sites will have their subjects return to the site for the end-of-RW assessment (EORW). Data cutoff will occur after all subjects have completed this assessment. All data for this cutoff will be used in the primary analysis for efficacy and safety.

After the RW period, there will be a Long-term Extension Treatment period. An analysis will also be conducted after the end of the study. Since the data cutoff for the primary analysis will be done by the end of RW period, summary for LTE period will not be included in the primary analysis.

No interim analysis for claiming efficacy is planned. Interim safety review will be conducted by a Data Monitoring Committee (DMC). The analysis will be performed by a designated CRO. Details are in DMC charter and DMC Statistical Analysis Plan (SAP).

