5.2.1.2. Analysis Methods for the Primary Endpoint

The log rank test will be the primary method for the analysis of time to recurrence based on CEC confirmed events, stratified by the stratification variables for randomization. Analysis based on the ITT analysis set will be used as the primary analysis. Analysis based on the PP analysis set will be considered as a sensitivity analysis.

Time to recurrence will be summarized with the 25th, 50th (median), and 75th percentiles using the Kaplan-Meier (KM) method. The 95% confidence interval (CI) for the percentiles will be calculated using a log-log transformation. The percentage of subjects with pericarditis recurrence and its 95% CI will be calculated at weeks 8, 16, 24, and 36 since randomization, using Greenwood's formula with a log-log transformation.

The hazard ratio for KPL-914 vs. placebo and the corresponding Wald 95% CI will be calculated based on a Cox proportional-hazards model with treatment as covariate, stratified by randomization strata.

A sensitivity analysis will be performed based on the Investigator's judgement of pericarditis recurrence. A 2×2 table for the concordance/discordance between Investigator's judgement and CEC's adjudication will be generated.

Upon pericarditis recurrence as determined by the investigator, subjects who report at least 1 day with pericarditis pain measurement ≥ 4 on the 11-point NRS and have 1 CRP value ≥ 1 mg/dL (either on the same day or separated by no more than 7 days) will receive bailout rilonacept (2 open-label injections of 160 mg rilonacept [or 4.4 mg/kg for pediatric subjects]) irrespective of randomized treatment assignment and as soon as at least 5 days have passed since the last study drug injection. The subjects transitioning to bailout rilonacept will remain blinded to their randomized treatment assignment.

For subjects who have pericarditis recurrence, the frequency table and listing will be generated for the following treatment prescribed by the Investigator:

- Bailout rilonacept
- Analgesics
- NSAIDS
- Colchicine
- Other.

The following criteria for pericarditis recurrence were provided to CEC to determine pericarditis recurrence:

1. Re-appearance or worsening of typical pericarditis pain (with at least one pain NRS recording ≥ 4) AND elevated CRP (≥ 1.0 mg/dL) either on the same day or separated by no more than 7 days

OR

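### The Week 24 KM difference (endpoint 7) has no rule for a placebo curve at 0 or with nobody at risk, so its normal-approximation p-value and CI are unreliable and tend to be anti-conservative

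*SAP*

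**What the plan says.** Endpoint 7 (SAP v2.0, section 5.2.2.3) estimates the Week 24 recurrence-free proportion in each arm by Kaplan-Meier under the primary censoring rules. It takes the variance of the difference as the sum of the two arm variances. Then: "The p-value and 95% CI will be calculated using a normal approximation".

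The length of the RW period depends on the event count (section 2.4): "When at least 22 adjudicated pericarditis recurrence events have occurred, end of RW period will be announced". No minimum follow-up is stated there. Section 2.3.1 plans about 50 randomized subjects or more and anticipates no more than 100 enrolled. It gives no accrual rate.

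For the per-arm recurrence percentages, section 5.2.1.2 uses intervals "calculated at weeks 8, 16, 24, and 36 since randomization, using Greenwood's formula with a log-log transformation".

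No sentence covers a KM estimate of 0, or an arm with nobody at risk, at Week 24 or Week 36. The qualifier in section 3.1 about results being estimable is attached to the time percentiles. Section 3.3 sets every RW treatment comparison at one-sided 0.025, but its gatekeeping and Hochberg procedure covers only the primary and three major secondary endpoints. Endpoint 7 lies outside it.

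**The concern.** A fixed-time KM comparison needs subjects under observation at that time. Here the expected placebo curve is low by Week 24 and the period may close before many subjects could reach it. Two things can then go wrong.

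- The last placebo subject under observation has an event before Week 24. The curve drops to 0 and its Greenwood variance is zero or undefined. The summed variance then reflects the rilonacept arm alone, so the standard error is too small.
- The last placebo subject is censored before Week 24. No Week 24 estimate exists unless the curve is carried flat.

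Applied as written, the rule still tends to produce a p-value and a CI. The risk is an easily quoted 24-week difference with too small a p-value and too narrow an interval.

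**Working it through.** **1. The plan's event count.** Inputs from section 2.3.1: "1-sided significance level: 2.5" per cent, 90% power, and "Hazard ratio (rilonacept/placebo): 0.244". Schoenfeld formula, 1:1 allocation:

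d = 4(1.960 + 1.282)² / (ln 0.244)² = 4 × 10.51 / 1.990 = 21.1, so 22.

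This agrees with the plan: "a total of 22 adjudicated pericarditis recurrence events is required to achieve the power". Power at 22 events is 0.911.

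**2. Expected curves.** Inputs: "Time to pericarditis recurrence is assumed to follow an exponential distribution" and "Median time to event (in weeks) in placebo: 8".

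- Placebo S(24) = 0.5^(24/8) = 0.125. Rilonacept S(24) = 0.125^0.244 = 0.602.
- With complete 24-week follow-up, 25 × 0.125 = 3.1 placebo subjects remain.
- At Week 36, placebo S(36) = 0.5^(36/8) = 0.044, so 25 × 0.044 = 1.1 remain.

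Event-driven closure can only lower these counts.

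**3. Why the variance fails.** Greenwood: Var = S² × Σ d/[n(n − d)]. When the last subject at risk has the event, n = d = 1. That term is 1/(1 × 0), and S² = 0. The result is undefined, or zero by convention.

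**4. Simulation.** 50 randomized, exponential times, closure 2 weeks after the 22nd event. Assumptions not in the SAP: uniform randomization over the stated accrual, the 2-week lag, no dropout. A zero-variance arm contributes 0. *All trials* carries the curve flat when nobody is at risk. *Estimable* keeps trials in which each arm either has someone at risk at Week 24 or has already reached 0.

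| Accrual (weeks) | 26 | 52 | 78 | 104 |
|---|---|---|---|---|
| **HR 0.244** | | | | |
| Mean placebo at risk, Week 24 | 0.64 | 1.22 | 1.41 | 1.46 |
| No placebo subject at risk | 58% | 31% | 24% | 23% |
| Placebo KM = 0 | 22% | 21% | 19% | 19% |
| CI coverage, all trials | 0.89 | 0.90 | 0.92 | 0.92 |
| CI coverage, estimable | 0.87 | 0.91 | 0.92 | 0.93 |
| **HR 1, both medians 8 weeks** | | | | |
| One-sided rejection, all trials | 0.085 | 0.049 | 0.041 | 0.037 |
| One-sided rejection, estimable | 0.055–0.060 | 0.062 | 0.043–0.049 | 0.040 |
| CI coverage, all trials | 0.82 | 0.91 | 0.92 | 0.92 |

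At HR 0.244 the difference is not estimable in about 39%, 9% and 5% of trials (26, 52, 78 weeks). With the same design and accruals of 13 to 78 weeks, the log-rank test rejects 2.4–3.0% at HR 1.

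**5. Which part is at fault.** Keep only trials in which both KM estimates lie strictly between 0 and 1 (42%, 71%, 76% at HR 0.244; accrual 26, 52, 78 weeks):

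- Plain interval, coverage: 0.937, 0.938, 0.946.
- Log-log limits combined by square-and-add (MOVER), coverage: 0.951, 0.939, 0.944.
- Plain test at HR 1: rejection 0.011, 0.007, 0.008, which is conservative (these are only 1%, 28% and 40% of trials at HR 1).

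So the shortfall comes from trials with KM = 0. The choice of scale matters little.

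**6. Sensitivity.**

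- Closure waits until all 50 are randomized over 52–78 weeks: 1.8–2.2 placebo subjects at risk, coverage about 0.92, rejection 0.035–0.043. Over 26 weeks it is 0.7 at risk, and rejection at HR 1 is 0.10, but only 37% of those HR 1 trials are estimable.
- Closure waits until 86 are randomized over 52–78 weeks: 3.0–3.8 at risk, coverage 0.93–0.94, rejection 0.030–0.037.
- 86 planned over 78 weeks, closure still at 22 events: 0.6–1.2 at risk, coverage 0.89–0.91, rejection 0.057.
- Both arms with median 8/0.244 = 32.8 weeks: about 9–12 at risk per arm, rejection 0.026–0.035.

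**The case against.** The strongest reply has four parts.

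- **The trigger does not fix the number at risk.** The SAP says at least 22 events and 50 subjects or more, and states no accrual. It also expects follow-up past Week 24: an ITT Week 24 set, later 8-weekly visits, percentages at Week 36. This stands. A reader might infer that the 22-event rule by itself leaves one or no placebo subject at Week 24. The documents do not support that; it depends on accrual and on how many are randomized before closure.
- **The normal approximation is not the culprit.** A summed-variance interval is an ordinary choice for a difference, and the log-log interval of 5.2.1.2 belongs to a single survival probability. This stands, on step 5. A reader might infer that carrying the log-log transformation over would cure the problem. It would not, because it is also undefined at KM = 0.
- **The inflated error comes from simulation conventions.** Partly right: zero variance and flat carry-forward are conventions, not SAP rules. But the SAP supplies no other rule, and the estimable-only results err in the same direction.
- **The consequence is small.** This stands as to confirmatory claims. Endpoint 7 carries no alpha, and the primary log-rank test already addresses recurrence.

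**Conclusion.** The point holds as a gap in the rule for a descriptive-level result. On the SAP's planning assumptions, with accrual assumed at 26–104 weeks, the Week 24 placebo estimate often rests on one subject or none and is 0 in about a fifth of trials. The p-value and CI are then unreliable and tend to be anti-conservative: coverage about 0.87–0.93 at the design hazard ratio, and all-trials rejection of about 0.03–0.05 for accrual of 52 weeks or more (0.062 at 52 weeks if only estimable trials count), against 0.025.

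A reader might infer a false-positive rate of two to four times nominal in general. The upper part of that range appears only with fast accrual; the effect is moderate over a year or more, and small with more subjects randomized before closure or a lower event rate. Nor is any confirmatory conclusion at risk: the primary and major secondary tests do not use this rule.

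**What to change.** Amend endpoint 7 in section 5.2.2.3, with a matching line in 5.2.1.2:

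1. Delete the normal-approximation p-value and let the stratified log-rank test of the primary endpoint carry the inference on recurrence.
2. Report the number at risk in each arm at Week 24.
3. State that the Week 24 difference and its CI are not estimable when an arm's KM estimate is 0 or no subject in it remains at risk. Apply the same rule to the Week 36 percentages in 5.2.1.2.
4. Give the per-arm log-log intervals of 5.2.1.2 wherever they exist.

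The rule in item 3 is the essential part; changing the interval method alone would achieve little. The cost is SAP wording and a few lines of code. The downside is the loss of one p-value outside alpha control, and a Week 24 difference that may have to be reported as not estimable.
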